## **STATEMENT OF COMPLIANCE**

The study will be conducted in accordance with the International Council for Harmonisation guidelines for Good Clinical Practice (ICH E6), the Code of Federal Regulations on the Protection of Human Subjects (45 CFR Part 46), and the NIDCR Clinical Terms of Award. All personnel involved in the conduct of this study have completed human subjects protection training.

## LIST OF ABBREVIATIONS

AE	Adverse Event/Adverse Experience
ASA	American Society of Anesthesiologists
CFR	Code of Federal Regulations
CRF	Case Report Form
DCC	Data Coordinating Center
EC	Experimental Care
eCRF	Electronic Case Report Form
FDA	Food and Drug Administration
FFR	Federal Financial Report
GCP	Good Clinical Practice
HIPAA	Health Insurance Portability and Accountability Act
ICF	Informed Consent Form
ICH	International Council for Harmonisation
ICMJE	International Committee of Medical Journal Editors
IRB	Institutional Review Board
ISM	Independent Safety Monitor
MOP	Manual of Procedures
N	Number (typically refers to subjects)
NIDCR	National Institute of Dental and Craniofacial Research, NIH, DHHS
NIH	National Institutes of Health
OCTOM	Office of Clinical Trials Operations and Management, NIDCR, NIH
OHRP	Office for Human Research Protections
OMS	Oral and Maxillofacial Surgeons
PHI	Protected Health Information
PI	Principal Investigator
QA	Quality Assurance
QC	Quality Control
RJ2	Restful Jaw/ jaw support device
SAE	Serious Adverse Event/Serious Adverse Experience
TMD	Temporomandibular Disorders
UP	Unanticipated Problem
UC	Usual Care
US	United States

WHO

World Health Organization

[figure not shown]
## PROTOCOL SUMMARY

Title:	The Restful Jaw Device: A New Way to Support and Protect the Jaw During Third Molar Extractions
Précis:	
During mandibular 3rd molar (wisdom tooth) extractions, when a downward force is placed on the patient's jaw, the patient must tense his/her jaw muscles to oppose it. Patients under moderate/deep sedation or general anesthesia cannot tense their muscles to counter this downward force to prevent injury to the jaw including the temporomandibular joint (TMJ). Bite blocks hold the patient's mouth open but do not counter this downward force on the mandible. In this two-arm parallel randomized clinical trial (RCT) design, 294 patients undergoing 3rd molar extractions with moderate/deep sedation or general anesthesia will be randomly allocated to Usual Care (UC) or Experimental Care (EC). The study intervention for EC is use of the Restful Jaw version 2 (RJ2) device, which supports the jaw during the extractions, with concurrent use of a bite block. The study control is UC, which involves the dental assistant supporting the jaw during the extractions with concurrent use of a bite block. Patients will report temporomandibular disorders (TMD) pain via questionnaires at baseline and the 1-, 3-, and 6-month follow-up time points.

Objectives:	
Primary: In patients undergoing mandibular 3rd molar extractions with moderate/deep sedation or general anesthesia, compare the incidence of TMD pain within a 6-month follow-up period between the two groups:
 

• UC group, using a bite block and with hand support of the jaw, and

• EC group, using a bite block and the RJ2 device to support the jaw.

 
The primary outcome is the incidence of TMD pain within a 6-month follow-up period (binary dependent variable).
 
The secondary objectives of this study are to:

1. Compare the incidence of TMD pain between UC and EC groups using an alternate assessment instrument to identify TMD pain within a 6-month follow-up period
2. Compare TMD pain intensity between the UC and EC groups within a 6-month follow-up period: at 1-, 3- and 6 months.
3. Compare TMJ noise, pain characteristics (e.g., location in temple or jaw, and occurrence with wide opening of mouth) and change in jaw pain since it started, within a 6-month follow-up period: at 1-, 3- and 6 months.
4. (Exploratory Objective) Describe the experiences of surgeons and dental assistants with the new device at mid-way through recruitment of patients and at the end of recruitment.

Population:	Approximately 294 healthy, consenting adult patients, age 18-30, requiring surgical removal of bilateral mandibular 3 rd molars (concurrent maxillary 3 rd molar extractions allowed).
Number of Sites:	Approximately 4 clinical sites and 1 data coordinating center (DCC).
Description of Intervention:	The RJ2 device is used to support the jaw during dental procedures including surgical removal of 3 rd molars (wisdom teeth) with moderate/deep sedation or general anesthesia. The device is designed to counter the downward forces placed on the mandible by clinicians during dental procedures and prevent jaw hyperextension (opening too wide) while providing a secure, stable jaw position. The RJ2 device has been determined by the Food and Drug Administration (FDA) to be a non-significant risk device.
Study Duration:	Approximately 36 months.
Subject Participation Duration:	Approximately 6 months.
Estimated Time to Complete Enrollment:	Approximately 14 months.

## 2 INTRODUCTION: BACKGROUND INFORMATION AND SCIENTIFIC RATIONALE

### 2.1 Background Information

Dental procedures can cause jaw pain, discomfort and fatigue from opening the mouth too long or too wide, or by placing too much force on the jaw. (1-15) Opening too wide can also cause hyperextension of the jaw. During and after long dental procedures, patients frequently report jaw pain, fatigue, or discomfort. This pain and dysfunction characterizes temporomandibular disorders (TMD), which can be short-term or may become chronic. TMD occurrence is frequently associated with trauma from dental procedures, including 3rd molar extractions. (1-15) Also, dental procedures may aggravate pre-existing subclinical TMD symptoms. (16)

Over 10 million 3rd molars (wisdom teeth) are extracted from about 5 million people in America each year.(1) More than 11 million patient days of “standard discomfort or disability” – pain, swelling, bruising and malaise – result postoperatively.(1) Although the American Association of Oral and Maxillofacial Surgeons guidelines state that consent forms for 3rd molar extractions should include injury to the temporomandibular joint (TMJ) or associated muscles(17), there are few reports of the trauma to the TMJ or jaw muscles from this procedure.(1) One of the best studies assessing development of TMD after 3rd molar extractions is a large prospective cohort study of young adults.(3) Huang et al. assessed the onset of jaw joint symptoms (i.e., TMJ noise and jaw pain) in individuals who had 3rd molar extractions compared to those who did not. Of the 517 participants with follow-up data, 39% (n = 201) had a total of 720 3rd molars extracted, with 68% reporting that 'intravenous sedation' or general anesthesia was used. Among patients undergoing 3rd molar removal, the rate of TMD lasting more than 1 month was 34.3 per 100 person-years compared to 8.8 among those who did not have 3rd molar extractions. The relative risk of developing TMD was 3.8 and the rate of TMD reported by patients undergoing this surgery was greater than 30%. This study's findings are limited by its low follow-up rate (40 to 50% for follow-up questionnaires at different intervals). Further, a retrospective study reported that almost a quarter of new onset TMD cases in young adults were associated with 3rd molar removal.(2) In a cross-sectional study of patients aged 18.7 + 1.1 years, the occurrence of 3rd molar extractions was significantly associated with TMD ( $P<0.001$ ). (7) Finally, in an age and sex matched case-control study, at 6 months follow-up, patients who had 3rd molar extractions had significantly more TMJ and jaw muscle pain than controls who did not have this surgery ( $P<0.05$ ). (6) These findings suggest removing 3rd molars is associated with development of TMD and that this patient safety issue is not addressed by current methods to protect the jaw during this surgery. Providing better support for

the jaw during 3rd molar extractions to prevent hyperextension and excessive force on the jaw would be expected to alleviate the physical stress on the jaw and reduce patient suffering and jaw injury. (18, 19)

## 2.2 Rationale

This study will test whether the new RJ2 device, when supporting the jaw during surgical removal of 3rd molars, reduces the incidence of TMD pain compared to usual care where the dental assistant supports the jaw. **Hypothesis:** The risk of developing TMD pain in patients undergoing 3rd molars (wisdom teeth) removal in the experimental care (EC) group will be statistically lower than in the usual care (UC) group within the 6-month follow-up interval.

**Rationale:** When a downward force is placed on the patient's jaw to surgically remove the mandibular (lower) 3rd molars, the patient must tense his/her jaw muscles to oppose it. This can result in jaw pain, discomfort or fatigue, especially if the force is high or prolonged. Patients under moderate/deep sedation or general anesthesia cannot tense their muscles to counter this downward force to prevent injury to the jaw. Bite blocks hold the patient's mouth open but do nothing to counter this downward force on the jaw. Opening a patient's mouth too wide can cause jaw hyperextension; a long extraction procedure time can also lead to injury of the jaw. This can result in patient suffering, lost time for the dentist to manage the symptomatic patient, and potential medico-legal problems. Currently, oral and maxillofacial surgeons (OMSs) when surgically removing 3rd molars (wisdom teeth) with moderate/deep sedation or general anesthesia have at least 2 dental assistants present. The first dental assistant provides suction and gives the surgical instruments to the surgeon. The second dental assistant is a certified anesthesia dental assistant who monitors the patient's vitals as well as oxygen and carbon dioxide levels while providing the patient with medications intravenously. This second dental assistant also inserts the bite block and then stands behind the chair and places their hands on both sides of the jaw to support it and oppose the downward force on the patient's jaw during the extractions. If additional intravenous medications are needed during the surgery, the surgery has to stop (lost time) and the OMS or the first dental assistant supports the jaw until the second dental assistant completes the medication administration. Based on clinical experience, the second dental assistant often experiences fatigue and pain in their hands, arms, neck and shoulders during long or difficult procedures, which can affect his/her ability to support the jaw. Given the second dental assistant's many duties and responsibilities, it is hard for the assistant to provide constant good jaw support while anticipating the direction and amount of force placed by the OMS on the patient's jaw during 3rd molar surgical removal. This may

explain the finding that almost a quarter of new onset of TMD cases in young adults is associated with 3rd molar removal. This **patient safety issue** can be addressed during 3rd molar surgical removal by using a bite block to hold the mouth open and concurrently using a jaw support device under the jaw to provide a stable counter force to downward forces on the jaw, thus preventing jaw hyperextension and injury to the jaw. This would also free the second dental assistant from holding the jaw so he/she can concentrate on his/her other duties, which would **improve patient safety**.

The currently patented **Restful Jaw® 1** (RJ1) device is designed to support the jaw when downward forces are placed on it and it has been shown to significantly reduce jaw pain during dental procedures ([restfuljaw.com](http://restfuljaw.com)). However, significant changes have been recommended by users of the RJ1 device who utilize moderate/deep sedation or general anesthesia. We have addressed these concerns and suggested changes in Phase I of this small business grant with an innovative design for the new **Restful Jaw 2** (RJ2) device (see Section 6 for a description of the new device). These changes included providing support on both sides of the jaw which mimics the dental assistant's placement of his/her hands. Also, the device attaches to the dental chair head post so the only contact to the patient is under his/her jaw. Finally, if the device needs to be removed from the patient during the procedure, the dental assistant presses on the foot pedal or the quick release control box and this deactivates the device so it can be quickly removed from the surgical field and away from the patient. Specifically, in Phase I step 1 of this grant, the OMSs and dental assistants (DAs) provided us with critiques of the prototypes of the RJ2 device. Then during Phase I step 2, they used a working prototype of the device on consenting patients having 3rd molar surgical removal with moderate/deep sedation or general anesthesia and provided additional feedback on the device. We continued this process to the point of saturation where we are confident the device is satisfactory for use in the oral surgery environment with the minor modifications which have been incorporated in the design.

## 2.3 Potential Risks and Benefits

### 2.3.1 Potential Risks

There are potential risks of using the RJ2 device. If excessive force is placed on the device by the OMS, then the device could slide to a slightly different position. However, as soon as this force is stopped, then the device will stop moving. There is potential that the device could malfunction and lose pressure during the procedure. If this occurs, the passively controlled arms will fall away from the patient's jaw which could also compromise the support of the patient's jaw. To mitigate these risks, the dental assistant will be present behind the dental chair to support the jaw. Patients have similar

risk of jaw injury when their jaw is supported only by the dental assistant's hands since their hands can slip in position if excessive force is placed on the jaw, and their supporting arms and hands can become fatigued during procedures compromising their ability to support the jaw. In addition, patients could report that the padded jaw brace when placed under their jaw feels uncomfortable. If this occurs, then the dental assistant can reposition the brace to a position that is comfortable. There are no other anticipated safety risks to participating in this study beyond those risks inherent in 3rd molar extractions with moderate/deep sedation or general anesthesia. Patients do not receive 3rd molar extractions as a study procedure. Consequently, risks of 3rd molar extraction with moderate/deep sedation or general anesthesia will be discussed with the patient as part of normal clinical care and are not considered to be study-associated. Finally, if any adverse event (AE) occurs, then it will be documented and assessed by the study team.

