**OMS and DAs – During data collection phase:**

- Both the OMS and any DA(s) who assisted in the procedure(s) and was responsible for using the device during the procedure, and consented to study participation, will each complete a questionnaire about their experience with the jaw support device once during recruitment and once at the end of recruitment. This questionnaire assesses; 1) use of the device compared to a dental assistant holding the jaw, 2) ease and stability of device use, 3) provider's comfort and posture when using the device, 4) fit and manipulation of device before and during procedure, 5) ease of removal of device, 6) efficiency of procedure with device, 7) interference with working field when device is used, 8) airway support with device, 9) impact of dental assistant's other duties with use of the device, 10) use of device in future, 11) thoughts on minimizing injury during procedures, 12) overall opinion of device and 13) any suggestions for modification of the device.

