### 12.3.1 Safety Review

If the device becomes loose or excessive force is placed on it during the procedure, there is a potential risk this could compromise the support of the patient's jaw, resulting in jaw injury.

While the proposed intervention does not include changes to practice that may harm patient participants, a special focus will be the safety of patients exposed to the study intervention.

We have no specific outcome measures related to safety but participating surgeons will be required to record all AEs, including SAEs, according to procedures specified in Section 9.2

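### Airway and sedation events are not described as solicited or pre-specified per patient in either arm, and the final analysis has no comparison of safety by arm

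*Combined protocol and SAP*

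**What the plan says.** **Risk and benefit.** Section 2.3.1 lists movement of the device under force, loss of pressure, and discomfort from the brace. It continues: "There are no other anticipated safety risks to participating in this study beyond those risks inherent in" the extraction under sedation or anesthesia, and it treats those background risks as not associated with the study. Airway support and access to the working field are not mentioned. Section 2.2 gives a safety rationale: "This would also free the second dental assistant from holding the jaw so he/she can concentrate on his/her other duties", which is said to make the patient safer. The same section says that this assistant "is a certified anesthesia dental assistant who monitors the patient's vitals as well as oxygen and carbon dioxide levels".

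**What staff are asked.** Section 8.1 (data collection phase) lists among the items on the staff questionnaire "7) interference with working field when device is used, 8) airway support with device", followed by the effect on the assistant's other duties. Each surgeon and assistant completes it once during recruitment and once at its end.

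**What is recorded per patient.** The content described for the Doctor Surgery Questionnaire (Section 8.1, OMS – Baseline) covers pain, joint noise, surgical details and, for device cases, whether the device was discontinued. No airway or sedation item is described.

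**Safety data and analysis.** Section 12.3.1 says "We have no specific outcome measures related to safety", while requiring surgeons to record all AEs and SAEs. Section 9.1.2 defines an AE broadly and regardless of relatedness; Section 9.2 starts recording at consent. Section 9.5 has a Fisher's exact test between groups on *Any AE* and *Any SAE* as a stopping rule. Section 12.3 plans no interim analysis. Section 12.4 contains no safety analysis.

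**The concern.** The experimental arm replaces the assistant's hands with a pneumatically locked brace under the jaw of a sedated or anesthetized patient. Effects on the airway, and on the attention the assistant can give to monitoring, are natural questions, and the staff form asks both. But that form yields opinions per clinician about one arm's equipment. It cannot give a rate per patient or a contrast with usual care.

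If the device reduces jaw pain, readers will next ask whether it helps or hinders care under sedation. As planned, the answer would rest on adverse events reported without prompting by surgeons who know the arm, with no final comparison specified. A brief desaturation or an airway maneuver may or may not be judged an AE. When it is, sedation offers a ready alternative cause: Section 9.3.1 classes an event with an established alternate etiology as not related, and Section 9.1 focuses monitoring on unanticipated problems, which must be at least possibly related to the research.

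**Working it through.** **1. Setting the sections side by side**

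| Question | Where addressed | What it yields |
|---|---|---|
| Airway support with the device | Staff form, 8.1 | Opinion, twice per clinician, device only |
| Assistant's other duties | Staff form, 8.1 | Same |
| Device discontinued during surgery | Surgeon form, 8.1 | Per patient, device cases only |
| Airway or sedation event | General AE recording, 9.1.2, 9.2, 9.5, 12.3.1 | Per patient, both arms, not solicited |
| Safety by arm | 9.5 | Fisher test on *Any AE* and *Any SAE*, as a stopping rule |
| Safety by arm at the end | 12.4 | Nothing specified |

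Appendix A has no row for AE collection, and the lists in Sections 13 and 16.3 name no AE form.

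**2. Number of patients available**

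The plan's own figure reproduces. With 14% as the lower rate, relative risk 2.0 (28%), two-sided alpha 0.05, 80% power and pooled variance:

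n = [1.960·√(2·0.21·0.79) + 0.842·√(0.14·0.86 + 0.28·0.72)]² / 0.14² = (1.129 + 0.478)² / 0.0196 ≈ 132 per group.

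Then 264 / 0.90 = 293.3, rounded up to 294, or 147 per arm with 1:1 allocation. Items recorded on the day of surgery would not be subject to the 10% loss to follow-up, so 147 per arm is used below.

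**3. What solicited items could show with 147 per arm**

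The documents give no airway or sedation event rate. All rates below are assumptions.

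- Zero events in one arm, one-sided 95% upper limit: 1 − 0.05^(1/147) = 2.0%.
- Zero events in one arm, two-sided 95% upper limit: 1 − 0.025^(1/147) = 2.5%.
- Approximate 95% half-width for a risk difference, 1.96·√(2p(1−p)/147): ±5.0 points at p = 5%, ±6.9 at 10%, ±9.1 at 20%.
- Smallest split against zero with Fisher p < 0.05: 6 versus 0 (p = 0.030); 5 versus 0 gives p = 0.060.

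| Assumed rates | Fisher power, 147 per arm | Per arm for 80% power (normal approximation) |
|---|---|---|
| 1% vs 2% | 2% | 2319 |
| 1% vs 3% | 9% | 769 |
| 2% vs 4% | 9% | 1141 |
| 5% vs 10% | 29% | 435 |
| 10% vs 20% | 62% | 199 |
| 5% vs 15% | 79% | 141 |

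For rare events the trial can estimate and bound, but it cannot test usefully.

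**The case against.** Several stronger readings are tempting, and the documents do not support them.

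- *No airway or sedation event is measured.* Such an event meets the AE definition in Section 9.1.2, and all AEs are to be recorded from consent with no restriction by arm. Calling sedation risks unrelated to the study affects attribution, not capture. What stands is that these events are not described as solicited or separately defined.
- *There is no usual-care comparator.* Section 9.5 names a between-group test on *Any AE* and *Any SAE*, and Section 16.4 has participant safety reviewed about every six months. What stands is that the test is a stopping rule with no planned look, that its outcomes pool airway events with every other complaint, and that Section 12.4 reports nothing by arm.
- *The protocol says the device adds no risk.* It says that no other risks are anticipated, after naming three.
- *The staff form admits an expected harm.* Airway support is one of 13 usability topics. A neutral question shows that the subject was thought worth asking about, and no more.
- *Improved safety is a claim of the trial.* It is conditional rationale. Section 2.3.2 confines the stated benefit to TMD pain, and Section 3 has no safety objective.

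Two further points are fair. The case report forms are held outside the protocol, so an airway item that the protocol does not list cannot be excluded. And the FDA's non-significant-risk determination, the Medical Monitor's review, and the quick-release and emergency-removal provisions all bear on the level of risk. They do not supply a comparison between arms.

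**Conclusion.** The point holds as a gap in collection and reporting. Airway and sedation events are not described as solicited or pre-specified in either arm, airway support is sought only as staff opinion, and no final safety comparison is planned. The rationale that relieving the assistant improves patient safety is therefore untested by any planned outcome, and the risk statement is silent on a subject that the staff form raises. How far the assistant is relieved also needs reconciling, since Section 2.3.1 says "To mitigate these risks, the dental assistant will be present behind the dental chair to support the jaw".

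No figure in the plan is wrong on this point. If the items were collected, zero events among 147 patients would bound the rate at about 2.0% to 2.5%. Differences such as 10% versus 20% or 5% versus 15% would be seen with Fisher power of 62% or 79%, and rarer ones with power below 10%. This rests on assumed event rates, on all randomized patients having surgery with a completed surgeon form, and on the forms containing no item beyond those the protocol describes. It is a worthwhile, inexpensive improvement. It does not threaten the primary comparison.

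**What to change.** 1. Add yes/no items to the Doctor Surgery Questionnaire, worded identically for both arms and drawn from monitoring already in place: oxygen desaturation, by a definition the sponsor sets, and any airway maneuver.
2. If interruption of surgery is also recorded, record its reason. Section 2.2 says that hand-supported surgery already stops when more intravenous medication is needed. Counting those routine stops as safety events would load them onto usual care and favour the device.
3. In Section 12.4, report these items and all AEs and SAEs by arm, as counts and risk differences with exact 95% confidence intervals and no significance claim. Amend the statement in Section 12.3.1 to match.
4. Reconcile Section 2.3.1 with Section 8.1 by stating that the effect of the brace on airway support is being assessed. The consent form was not available for this review, so the sponsor should check whether its risk text needs the same change.

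The cost is a few fields on a form that surgeons already complete for every patient, one table, and a slightly less favourable risk statement. No visit, procedure or staff is added. Rewording the safety rationale in Section 2.2 is an editorial choice for the sponsor.
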